8 INTERVENTION DISCONTINUATION

8.1 Permanent discontinuation of the study intervention

The study intervention will be discontinued if:

- A participant has a seizure;
- There are signs or reports of inability to tolerate the intervention. Specifically, the participant will no longer continue with the intervention if the participant either reports or indicates upon questioning that a side effect (such as a headache) is not well tolerated despite self-treatment (e.g. severe in intensity and persists beyond the first week of treatment), or if the study physician feels it is in the participant’s best interest to discontinue with the intervention.
- Or, any other health or safety concern that contraindicates continuation, based on the judgment of the study physician.

Continued follow-up will occur in each of these cases. The participant will be closely monitored and treated for any medical or psychological consequences. The Study Coordinator will be responsible for phone follow-ups to check on the participant’s well-being and to collect follow-up AE information.

Such participants will be encouraged to return for all three post-intervention follow-up evaluations (Visits 13, 14, and 15). Except for the MRI scan (Visit 13), all other outcome

measures, safety assessments, and AE information would be collected at the three follow-up visits.

8.2 Temporary discontinuation of the study intervention

The intervention will be temporarily discontinued in case of a concern regarding safety or intolerance to rTMS.

Recognized safety concerns for eligible participants during intervention are:

- Insufficient sleep;
- Use of substances or medications that increase seizure risk.

Tolerability concerns include:

- In case of headache or site application discomfort or other AE, the intervention can be temporarily discontinued either at the request of the participant or based on a physician's recommendation.

Modifications to the intervention schedule. In the event of a safety concern, the Study Coordinator or TMS Operator will alert the Study Physician before proceeding with rTMS. If the participant reports having had less than one hour of sleep the previous night, the rTMS session will be postponed until the participant's sleep pattern improves. If it is determined that a participant is using or abusing substances or medications that increase risk of having a seizure, the Study Physician and PI will evaluate the situation and determine if it is appropriate for the participant to continue.

While a participant is temporarily discontinued from receiving the intervention, the Study Coordinator will be responsible for phone follow-ups to check on the participant's well-being and, if applicable, to collect information regarding resolution and/or occurrence of adverse events.

8.3 Replacement Subjects and Voluntary Withdrawals

Replacements. In the event of an SAE prior to the Baseline Visit or a medical emergency during a Baseline MRI, (i.e. prior to randomization), the intervention and study assessments will be canceled. Such a participant would continue to be followed to monitor recovery; however, active participation in the study would end for the participant's safety, and because of unstable or uncertain health status. (See also Appendix VII. "MRI Emergency Protocol" and Section 7 above.) Another subject will be enrolled to replace that participant.

Voluntary withdrawals. Subjects may withdraw voluntarily from participation in the study at any time and for any reason. If voluntary withdrawal occurs during the intervention phase, the participant will be encouraged to return for all three post-intervention follow-up evaluations (Visits 13, 14, and 15). Except for the MRI scan (Visit 13), all other outcome measures, safety assessments, and AE information would be collected at the three follow-up visits. If an AE or SAE begins during the intervention phase and the participant decides to withdraw, the Study Coordinator will continue to do phone follow-ups to check on the participant's well-being and to collect follow-up AE information.

9 STATISTICAL CONSIDERATIONS

9.1 General Design Issues

This is a double-blind, randomized, 2-stimulation-site, sham-controlled parallel group design of rTMS treatment to either bilateral DLPFC or LPC. The parallel groups design avoids potential carryover effects of active rTMS treatment to other treatment conditions within the same subject. The length of an appropriate washout period for rTMS has not been established for this rTMS intervention protocol in this population.

Primary Hypothesis

The primary hypothesis is that participants receiving active (“real”) rTMS will show more improvement in memory at the immediate post-treatment assessment than the placebo (sham) control group. The sham group is comprised of all subjects assigned to the sham group, regardless of the position of the sham coil.

Testing the primary hypothesis involves two statistical tests: Test 1 will compare Active DLPFC to sham; Test 2 will compare Active LPC to sham.

For these tests, memory is measured by the CVLT-II Trials 1-5 Total raw score. This outcome measure has excellent retest reliability (Total and Delayed: $r > .75$), diagnostic validity (Rabin et al., 2009) (Silva et al., 2012), and normative data on a representative sample. The CVLT, which is comprised of 16 concrete words presented for 5 learning trials, helps achieve a wide range of scores that are neither at floor nor at ceiling level (Ellis et al., 2009; Karrasch, Sinerva, Gronholm, Rinne, & Laine, 2005; Ribeiro, de Mendonca, & Guerreiro, 2006). An additional advantage of the CVLT-II is the availability of alternate test forms.

Secondary Analyses

This study, was originally proposed in response to NIH/NIA PAR-16-365 “Pilot Clinical Trials for the Spectrum of Alzheimer’s Disease and Age-related Cognitive Decline (R01).” In addition to testing the primary hypothesis to learn whether rTMS is a viable nonpharmacological intervention for treatment of MCI, this study was designed to address essential questions of durability, choice of site, and prediction of response. Information gained from this study will inform efforts to optimize rTMS effectiveness and pave the way for further clinical development. From this perspective, we plan to examine durability of rTMS over the 6-month follow-up, and to describe effects of rTMS on secondary cognitive and behavioral outcomes, as described below:

(Grant Aim 2a) Assess the durability of rTMS effects: The primary efficacy measure, the CVLT-II Trials 1-5 Total raw score will be analyzed for effects of rTMS on memory at 3- and 6-month post-intervention. Our working hypothesis is that an effect of rTMS on memory will be sustained up to 3 months.

(Grant Aim 2b.1) Examine behavioral differences related to the site of brain stimulation: The secondary behavioral outcomes will be analyzed in longitudinal data analyses with respect to the site of active stimulation (DLPFC or LPC). The secondary behavioral outcomes of most interest are selected sub-scores of the CVLT-II.

- Because the DLPFC and LPC have distinct roles in memory encoding and delayed recall (Long, Oztekin, & Badre, 2010), our working hypothesis is that DLPFC stimulation could result in a higher level of semantic clustering compared to LPC

stimulation. By contrast, LPC stimulation could result in higher recall, assessed by CVLT-II short- and long-delayed recall scores. An rTMS-induced increase in semantic clustering would be a positive outcome in MCI because older adults who showed more semantic clustering on the CVLT-II were more cognitively stable over time (McLaughlin et al., 2014). An rTMS induced increase in delayed recall would also be clinically important.

As part of addressing secondary Aim 2b.1, effects of rTMS on other secondary outcomes will be described. These outcomes include depressive symptoms, objective assessments of global cognitive function, visuospatial episodic memory, language, visuo-constructional ability, orienting of attention, information processing speed, executive function, and self-/partner-reported assessments of everyday cognitive functioning. All measures have demonstrated re-test reliability and construct validity. These secondary outcomes (which are described in Section 6.2.2) are listed in Section 9.4.2 below.

(Grant Aim 2b.2) Changes in brain function related to the site of brain stimulation.

This study is designed to provide novel information about the therapeutic mechanisms of rTMS in the target population. Resting-state fMRI scans will be acquired at the Baseline visit and the Immediate Post-Treatment visit to examine effects of rTMS on brain functional connectivity. Additionally, plasma levels of brain-derived neurotrophic factor (BDNF) will be measured before and at completion of the rTMS intervention.

- Our working hypothesis is that BDNF levels will increase more in either active rTMS group, compared to that in the sham group.
- Our working hypothesis is that rTMS will beneficially modulate functional connectivity within and between large-scale networks that are abnormal in MCI. Two analyses will be performed: (1) The aim of one set of analyses is to learn the extent to which rTMS can restore connectivity within regions of the Default-Mode Network (DMN), especially to the hypo-connected PCC; (2) The aim of the second set of analyses relates to between-network connectivity. We will examine if rTMS reduces abnormally strong functional connectivity between the Central Executive, and Default-Mode Networks (CEN and DMN), as has been found preliminarily in rTMS studies on ameliorating depressive symptoms in TRMDD and executive dysfunction in mild TBI. Functional connectivity metrics are outlined in Section 9.4.2 “Secondary neuroimaging outcomes.” Analyses are outlined in Section 9.5.2 “Secondary Analyses.”
- As part of addressing secondary Aim 2b.2, we will explore the extent to which rTMS-induced changes in functional connectivity correlate with changes in selected behavioral variables, e.g., is the amount of reduction in functional connectivity between the CEN and DMN associated with improvement in executive function?

(Grant Aim 2c) Heterogeneity of response to rTMS. We expect that baseline clinico-demographic characteristics, baseline connectivity, and genetic variants may help explain individual differences in responsiveness to rTMS, either generally, or to a particular rTMS site. Selected baseline variables relevant to explaining heterogeneity of response are outlined in Data Analysis Sections 9.5.2.

9.2 Sample Size and Randomization

Power to test the primary hypothesis. We have powered the proposed study to detect a moderately large effect size (Cohen's $d = 0.80$) of either rTMS treatment on the primary outcome. Moderately large effect sizes of 1.0, 0.80, and 0.80 were reported in two meta-analyses of rTMS studies in AD (Liao et al., 2015) (Hsu et al., 2015) and one rTMS trial in MCI (which used unilateral rTMS (Drumond Marra et al., 2015), deemed suboptimal by (Liao et al., 2015)). Our proposed design is estimated to have 80% power to detect an effect size of 0.8, for a 5% two-tailed test, with a multiple testing penalty for 2 tests.

Attrition and the test of the primary hypothesis. The attrition rate in [name] rTMS TBI trial at our site has been 0% so far. The rate of attrition in the rTMS MCI trial (Drumond Marra et al., 2015) due to all reasons was 6%. Based on these rates of attrition, we do not expect attrition to substantially reduce power or the interpretation of results. If a participant in the present study discontinues the intervention early, we will encourage the participant to undergo all post-intervention assessments that are normally administered during the Follow-up Phase (Visits 13, 14, and 15). If there are baselined participants who have missing outcome data, we will perform and report sensitivity analyses that include participants with missing data, and make plausible assumptions about their outcomes based on the observed data. Additionally, the total minutes of rTMS received by each participant can be used as a covariate in the data analyses.

Attrition and secondary data analysis of behavioral outcomes. For the durability analysis of rTMS effects, mixed-effect growth curve analyses will be used, which enables full utilization of repeatedly measured outcomes and minimizes bias if subjects drop out during the extended follow-up period of the study (Singer & Willett, 2003).

Likelihood of obtaining other useful secondary results. In these secondary analyses, the proposed sample size will provide 80% power to detect a large difference ($d = 1.00$) related to the site of stimulation. For all analyses, we will convey practical significance by reporting effect sizes and confidence intervals, in addition to reporting statistical significance.

9.2.1 Treatment Assignment Procedures

Participants will be randomized to one of three treatment groups: (1) active rTMS of the DLPFC, (2) active rTMS of the LPC, or (3) sham rTMS (evenly split between each coil location). An adaptive randomization scheme will be used so that equal numbers of participants will be randomized to each of the 3 treatment groups within blocks of every 6 participants. For each block, 4 active and 2 sham treatment numbers will be randomly assigned. To ensure proper allocation of participants, a block of 6 participants will consist of: 2 active DLPFC, 2 active LPC, 1 sham DLPFC and 1 sham LPC.

The treatment numbers are non-sequential, and a 6-digit number is assigned to each participant. This unique 6-digit number will be key entered into the TMS device interface, whose programming enables the device to deliver the appropriate treatment (active or sham) to that participant.

Masking. To ensure appropriate masking for the study, the Database Manager/SAS Programmer performs the randomization of each participant to treatment and maintains the randomization codes. The Database Manager will store the randomization codes in an encrypted restricted-access file on the server. Only the Database Manager will know the link for randomization. To prevent unplanned breaking of randomization codes, the

Database Manager will utilize codes to refer to treatment groups, and maintain the link of these codes to the actual treatment groups in a separate file.

Unmasking. If a participant were to experience an SAE during the intervention phase, unmasking of that participant's treatment is permitted only if knowledge of the participant's treatment assignment is necessary to protect patient safety. The DSMB will determine when they should be unmasked to treatment assignment for the reviewing of adverse event data.

9.3 Interim analyses and Stopping Rules

There is no planned interim analysis for this single-site project. The DMSB or NIA will determine if a planned interim analysis should be conducted. If the DSMB requests a detailed safety review of SAEs or severe AEs by group, then based on that review, the DSMB or NIA Officer will determine what steps will be taken.

9.4 Outcomes

Outcome measures will be collected by blinded staff (study coordinator, imaging analyst, laboratory staff), and analyzed at study completion by the Database Manager under the supervision of the Ph.D. biostatistician.

9.4.1 Primary outcome

Primary outcome is the California Verbal Learning Test (CVLT-II) Trials 1-5 Total raw score (possible range 0-80), assessed at Visit 13 (immediate post-treatment).

The CVLT-II is also assessed at Visit 2 (Baseline) and at Visits 14 and 15. As described in Sections 9.4.2 and 9.5. these scores will be used as the baseline covariates and secondary outcomes.

9.4.2 Secondary outcomes

a) Secondary behavioral outcomes (assessed at Visits 2*, 13, 14 & 15)

- Depressive symptoms: 15-item Geriatric Depression Scale (GDS), Total score (0-15)
- Everyday functional outcomes: Everyday Cognition Scale Total score (39-156) and Functional Activities Questionnaire Total score (0-30)
- Global cognition: Montreal Cognitive Assessment Total score (0 to 30)
- Verbal episodic memory: CVLT-II Semantic clustering (chance-adjusted) Trials 1-5 (0-80) and CVLT-II Short-delay free recall correct (0-16)
- Visuospatial episodic memory: Brief Visuospatial Memory Test-Revised (BVRT) Trials 1-3 Total raw score (0-36)
- Language: Category Fluency Total score & 42-item Boston Naming Test Total score (0-42)
- Visuoconstructional function: Rey-Osterrieth Complex Figure, Copy score (0-36)
- Speed of processing: Trail Making Test, Part B, number of seconds to complete and the Attentional Network Task (Alerting) correct reaction time (RT) (msec)
- Executive function: Attentional Network Task (Executive) correct RT (msec)
- Visuospatial orienting: Attentional Network Task (Orienting) correct RT (msec)

*GDS is assessed at the time of screening (Visit 1) because the GDS is an eligibility criterion. The visit 1 GDS score will also be treated as a Baseline score.

b) Secondary neuroimaging outcomes (assessed at Visits 2 and 13)

- Functional connectivity metrics (derived from the pre- and the post-intervention rs-fMRI scans) will be computed with respect to:
 - Connectivity within the DMN, and
 - Connectivity between the DMN and the CEN.
- Analyses are outlined in Section 9.5.2 “Secondary Analyses.”

c) Secondary biomarker outcome (assessed at Visits 3 and 12)

- Plasma levels of BDNF will be measured from fasting blood samples that are collected at the first and last morning intervention sessions of Visits 3 and 12.

9.5 Data Analyses

9.5.1. Primary Hypothesis Testing

- Analysis: Test the hypothesis that active rTMS (to either stimulation site) is superior to sham in improving memory performance, as observed at the immediate post-treatment visit.
- Method: Analysis of Covariance (ANCOVA)
- Population: Intention-to-treat (ITT), defined as all randomized patients who started at least 1 treatment session.
- Independent variable: rTMS Treatment group
 - ANCOVA 1: active DLPFC vs sham
 - ANCOVA 2: active LPC vs sham
- Dependent variable: Primary outcome, i.e. CVLT-II Trials 1-5 Total raw score at Visit 13
- Covariate: CVLT-II Trials 1-5 Total raw score at Baseline, i.e. Visit 2
- Results will be presented as n, mean and standard deviation of CVLT-II (Total Trials 1-5) scores at baseline and post-treatment. ANCOVA model parameters with estimates will be provided.
- The two tests of treatment effects will be conducted at a 2-sided alpha level of 0.05, adjusted for two tests; 2-sided confidence intervals will be displayed with a 95% confidence level.

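### Do 95% intervals shown beside multiplicity-adjusted primary tests undermine the primary result in section 9.5.1?

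*Combined protocol and SAP*

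**What the plan says.** Section 9.1 states that "Testing the primary hypothesis involves two statistical tests", one for each stimulation site against the pooled sham group. Section 9.5.1 makes them two separate two-group models, the first being "ANCOVA 1: active DLPFC vs sham" and the second the same for LPC, each with baseline CVLT-II as covariate. It then says the tests will be "conducted at a 2-sided alpha level of 0.05, adjusted for two tests; 2-sided confidence intervals will be displayed with a 95% confidence level".

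Section 9.2 states the power: "Our proposed design is estimated to have 80% power to detect an effect size of 0.8". The error rate behind that figure is described there only in general terms, as a two-sided 5% level with an unspecified penalty for testing twice. The same section says of all analyses that "we will convey practical significance by reporting effect sizes and confidence intervals, in addition to reporting statistical significance".

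Neither section names the adjustment (Bonferroni, Holm, Hochberg, Dunnett or another). Neither says whether the 95% level is per contrast or simultaneous.

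**The concern.** The sentence in 9.5.1 adjusts the tests and then gives the intervals the conventional level. Read plainly, each ANCOVA produces its own ordinary 95% interval, while its p-value is judged against a stricter limit. A site could then fail its primary test and still be shown with an interval wholly above zero. Because 9.2 commits to showing intervals beside significance, readers will see the two together. Because 9.5.1 frames success as superiority at either site, a reader could take one favourable interval as support for a site that failed. Two ordinary 95% intervals also cover both true effects together less than 95% of the time. Finally, an unnamed adjustment seems to leave room to choose among methods once the p-values are known.

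**Working it through.** **Inputs.** 33 per arm (Précis; section 3). Two contrasts sharing one sham arm (9.1). Two-sided 0.05 adjusted for two tests (9.5.1). d = 0.80 and 80% power (9.2). Attrition of 6% in the earlier MCI trial (9.2). Retest reliability above .75 for the CVLT-II (9.1). Assumptions: all 33 evaluable, Bonferroni at 0.05/2 = 0.025 unless stated, and baseline correlations of 0.5 to 0.75.

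**1. The plan's own figure.** Noncentral t power for two means, d = 0.8, two-sided:

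| n per arm | alpha 0.025 | alpha 0.05 |
|---|---|---|
| 31 (33 × 0.94 = 31.0) | 80.0% | 87.3% |
| 33 | 82.7% | 89.3% |

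The stated 80% fits 0.025 per test after 6% attrition. Section 9.2 does not say that 33 was reached this way, and a Dunnett limit (about 0.027 per test) would give nearly the same n. The figure is therefore consistent with a two-test penalty but does not identify the method.

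**2. The gap between test and interval.** Each ANCOVA has 66 − 3 = 63 df. With balanced baselines, SE = √(2/33) = 0.246 residual SD.

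- 95% half-width: 1.998 × 0.246 = 0.492
- 97.5% half-width: 2.296 × 0.246 = 0.565, which is 15% wider

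An estimate between 0.49 and 0.57 residual SD fails at 0.025 but has a 95% interval above zero. Example: p = 0.035 gives t = 2.155 and an estimate of 2.155 × 0.246 = 0.53. The 95% interval is 0.04 to 1.02 and the 97.5% interval is −0.03 to 1.10.

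**3. How often, for one contrast.** At d = 0.8 residual SD, the chance of p < 0.05 is 89.2% and of p < 0.025 is 82.7%. The difference, 6.5%, is the chance of landing in the gap.

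**4. How often, for the trial.** Simulation of 600,000 trials per scenario, fitting both ANCOVAs with the shared sham arm. Section 9.2 says only Cohen's d, so both readings are shown. In raw SD with baseline correlation r, the residual effect is 0.8/√(1 − r²). At r = 0.75 that is 0.8/0.661 = 1.21.

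| True effect | At least one interval disagrees with its test | Of these, neither site wins |
|---|---|---|
| Both sites 0.8 raw SD, r = 0.75 | 0.65% | 0.04% |
| Both sites 0.8 raw SD, r = 0.6 | 4.1% | 0.6% |
| Both sites 0.8 raw SD, r = 0.5 | 6.8% | 1.3% |
| Both sites 0.8 residual SD | 12.6% | 3.6% |
| One site 0.8 residual SD, other zero | 9.0% | 7.0% |
| Both sites 0.5 residual SD (not in the documents) | 21.4% | 12.2% |

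A repeat of 400,000 trials per scenario agrees within 0.1 percentage points. In the 12.6% row, 12.6 − 3.6 = 9.0 points are trials in which the other site has already won, so the either-site hypothesis is already met.

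**5. What the tests deliver.** With no effect at either site, familywise error is 4.6% for Bonferroni and Holm and 5.0% for Dunnett. Joint coverage is 91% for two plain 95% intervals and 95.4% for two 97.5% intervals.

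**6. Which element decides.** Section 9.1 defines the primary hypothesis through two tests. Section 9.5.1 attaches the adjustment to those tests and says only that intervals are displayed. Section 9.2 gives intervals the separate task of conveying practical significance. Nowhere does an interval decide success.

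**The case for a change.** The strongest case for a change is that it would be free and would settle two things before results are known. Matched intervals (97.5% with Bonferroni, or Dunnett for both) can never contradict their tests, and naming the method removes any later choice. The 91% joint coverage does not depend on the effect size, and the mismatch becomes common if the true effect is smaller than planned.

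Much of this is correct as description. The method is unnamed, the interval level is unlabelled, and the figures reproduce. Three things limit its force.

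- The 91% is a shortfall only against a promise of simultaneous coverage, which the plan does not make. If 95% was meant as simultaneous under a single-step rule, the mismatch is zero.
- Matching is not simply an improvement. It widens the intervals by 13% (Dunnett) to 15% (97.5%), and Dunnett would replace the two specified ANCOVAs with a three-arm model that assumes a common variance and slope. It does not suit every valid adjustment either: under Holm at d = 0.8 residual SD, 97.5% intervals disagree with their tests in 9.0% of trials, against 3.6% for plain 95% intervals.
- The room for choice is small. Bonferroni and Holm always agree on whether at least one site succeeds, since both require the smaller p-value to be below 0.025. In the 400,000-trial run with no effect at either site, taking the most favourable of Bonferroni, Holm, Hochberg and three-arm Dunnett after seeing the data gave a familywise error of 5.6%. Any one of them fixed beforehand gave 5.0% or less.

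What stands is that the final tables should name the adjustment and say what kind of interval is shown.

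**Conclusion.** No change to the plan is needed. Followed as written, 9.5.1 gives a sound primary conclusion: two adjusted tests, familywise error of 5% or less under any of the usual methods, and power consistent with the stated 80%. The interval question affects how a borderline result looks, not whether a site is declared effective.

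Its size depends on the unit of d. The closest reading of the documents is Cohen's d in raw SD, with a baseline correlation near the reliability figure in 9.1, where "This outcome measure has excellent retest reliability" precedes a value above .75. On that reading an interval disagrees with its test in about 0.7% of trials, and neither site wins in about 0.04%. The .75 is not tied to this population, so lower correlations are possible. If d is in residual SD the figures are 12.6% and 3.6%, and smaller true effects raise them further. All assume 33 evaluable per arm, Bonferroni tests and per-contrast intervals.

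Per-contrast 95% intervals beside adjusted tests are a fair choice on which competent statisticians differ. Naming the method and labelling the intervals is missing detail of the kind an analyst supplies in the table footnotes. The point would carry more weight only if an interval were used to claim success, and no section does that.
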